Effects of Unloader Bracing in Clinical Outcome and Articular Cartilage
Physiology Following Microfracture of Isolated Chondral Defects

Study Protocol

NCT02016300

December 13, 2011

Effects of Unloader Bracing on Clinical Outcome and Articular Cartilage Regeneration following Microfracture of isolated Chondral Defects

Background

The management of articular cartilage defects continues to be one of the most challenging clinical problems for orthopaedic surgeons. Articular cartilage is a highly organized tissue with complex biomechanical properties and substantial durability. However, it has a poor intrinsic capacity for healing, and defects resulting from trauma can result in considerable functional impairment and lead to subsequent joint degeneration and osteoarthritis.¹

Bone marrow stimulation through 'microfracture' is the most frequently used technique for treating small symptomatic defects of the articular cartilage in the knee. It is a technically straightforward procedure, and the costs are low compared with those of other treatment modalities. Microfracture involves perforation of the subchondral plate in order to recruit mesenchymal stem cells from the bone marrow space into the lesion². The formation of a stable blood clot that maximally fills the chondral defect is important, and it has been correlated with the success of bone marrow stimulation procedures¹.

Two aspects of post-operative rehabilitation are thought to be critical to the success of microfracture. First, protected weight-bearing for 8 weeks post-operatively protect the clot from shear forces, which may disrupt the clot and prevent healing.^{3,4} Second, continuous passive motion is believed to encourage stem cell differentiation along a chondral pathway.^{4,5}

During rehabilitation following microfracture, an unloading valgus brace may further enhance clot stability by protecting it from disruptive shear forces during motion. Unloader braces apply an external, valgus force by creating a three-point bending moment along the knee, which decreases the force on the medial compartment.

The aim of this pilot study is to determine whether the use of post-operative unloading brace will improve outcomes of the microfracture procedure for treatment of isolated cartilage lesions.

Study Design (Pilot Study)

Recruitment

A pilot study will be carried out at two centers. 20 patients will be enrolled at each center and be randomized to 2 groups. Patients will be identified from preoperative clinical and radiographic evaluation as potential candidates for the study, however as eligibility will depend on arthroscopic assessment of the cartilage lesion at the time of surgery final enrollment will occur immediately post operatively.

Inclusion criteria include a discrete, contained chondral defect less than 2cm² in size located on the medial or lateral femoral condyle, age between 18-40 years, and overall neutral lower limb mechanical alignment (<5 degrees varus or valgus). Exclusion criteria include previous chondral procedures, osteoarthritis (Kellgren-Lawrence Grade ≥ 2), or significant concomitant knee pathology such as a meniscal tear requiring treatment or a ligamentous instability. Patients who have previously undergone ACL reconstruction or meniscal repair will still be eligible for inclusion in the study.

Initial post-operative protocol

All patients will participate in physical therapy two times per week, use a continuous passive motion device for eight weeks and will have no ROM restrictions. Following enrollment, 10 patients will be randomized into one of two groups at each center. Group 1 will be fitted with the Ossur Unloader One brace. Group 2 will be treated without a brace. At Center 1 (USA), patients will be initially kept non-weight bearing for a period of 8 weeks prior to applying an unloader brace. At Centre 2 (Japan), patients will wear an off-loading brace and commence weight bearing immediately post-operatively. Non-bracing group will be NWB for 8 weeks at both centers.

Outcome Measures

Radiographic outcome will be assessed using baseline, 6 month, and one and two year MRI scans which will assess the quality of the cartilage repair. T1 Rho and T2 mapping will be used to assess regenerate cartilage composition compared to surrounding normal cartilage, surface integrity, average cartilage thickness and the percentage to which the defect is filled. MRI mapping protocols investigate cartilage health by looking at glycosaminoglycan (GAG) concentration. Higher concentrations of GAG generally indicate healthier cartilage. Moreover, correlations have been found between T2 values and cartilage hydration, collagen fiber orientation, and loss of type 2 collagen, suggesting some degree of specificity for targeting the spatial collagen architecture of the matrix.⁶

Clinical outcome will be assessed at MRI follow-up time points using: The **Knee injury and Osteoarthritis Outcome Score (KOOS)** questionnaire is a standard clinical tool used to evaluate short-term and long-term symptoms and function in subjects with knee injury and osteoarthritis. It is broken up into five subcategories: Knee symptoms, knee pain, Function in daily living (ADL), Function in Sport and Recreation (Sport/Rec), and knee-related Quality of Life (QOL). The KOOS is a validated, reliable and responsive self-administered instrument that can be used for short-term and long-term follow-up of osteoarthritis and will be given to our patients to evaluate the effect of the unloading braces. The KOOS incorporates the commonly used WOMAC survey.

Tegner activity level scale will be used to establish standardized activity levels pre and post treatment. **VR-12** quality of Life questionnaire will be used to establish changes in quality of life. **Lysholm** score will be used to reflect symptoms with activities of daily living. **VAS (Visual Analog Scale)** will be used to determine the level of patient pain at each visit.

Schedule of Appointments

Visit 1 (T=0)

Visit 1 will be the baseline visit and will take place at the first post operative visit. Participants will undergo the informed consent process. Once signed, participants will answer standardized questionnaires (see above), get fitted for the brace (if in bracing group), and undergo baseline MRI scans and x-rays to evaluate alignment. Wearing of the brace will commence at the time of weight bearing, which will occur immediately post-operatively in Centre 2 (Japan) and 8 weeks post operatively at Centre 1 (USA).

Brace fitting

Each participant will be fitted by a licensed orthotist for the Unloader brace.

Imaging

Each participant will undergo a pre-study series of X-rays that are standard for osteoarthritis examination. This series consists of a front-view (AP) X-ray of the knees, a sideways (lateral) view, and a one with the knee flexed at 45° (Rosenberg). There will also be a long standing X-ray (36") that will film the lower extremities. These films will measure any mal-alignment present.

A MRI scan during the first visit will examine cartilage physiology. The scans will take place at the Stanford Medical Outpatient Center or Stanford Medical Lucas Imaging Center with a 3T scanner. Subjects will undergo 2D-T2 mapping, 3D-T2 mapping, and 3D-T1rho mapping. These scans take approximately 12, 10, and 6 minutes, respectively. The total time for the first visit will last approximately 2 hours.

Brace wear and documentation

All patients will be provided with a hard copy bracing diary for the 6-month study duration. Patients will be instructed to document the number of hours for which they wear the brace each day. Diaries will be collected at Visit 2 and daily and weekly averages will be calculated for all patients.

Each Unloader brace will be equipped with an iButton temperature sensor that acquires temperature readings every 20 minutes to objectively document brace wear. The temperature threshold to determine brace wear is set at 25C. The iButton captures and stores these measurements for 1 month after which it must be reprogrammed; all participants will therefore undergo five iButton swaps. These visits will be managed by the orthotist who performs the initial brace fitting. The final iButton will be obtained at Visit 2. iButton data files will be post-processed by [name] and daily and weekly averages calculated for each participant. These values will be compared with the bracing diaries completed by each patient.

Visit 2 (T=6 Months)

Visit two will consist of quantitative MRI scans conducted at the Stanford Medical Outpatient Center or the Stanford Lucas Imaging Center. The patient will also complete the same standardized questionnaires as in the first visit.

Visit 3 (T= 12 months)

The patient will return for another quantitative MRI scan and to answer the standardized questionnaires.

Visit 4 (T= 24 months)

The patient will come back again for a final MRI mapping scan and to answer the standardized questionnaires.

Benefits

All subjects requiring bracing will receive a fitted Unloader One off the shelf brace as compensation for their participation in the study.

Budget

Standard treatment costs, which the study sponsor will NOT be responsible for, include:

1. office visits

2. standard x-ray series
3. off-loader bracing (insurance reimbursement portion)

Sponsor study costs (per study site):

Year 1:

1. Any patient costs for Unloader brace NOT covered by insurance (unknown)

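### If both planned centres are analysed, the SAP's single group contrast averages two different regimen comparisons and does not estimate the effect of the brace alone

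*Protocol*

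**What the plan says.** Protocol, Recruitment: "20 patients will be enrolled at each center and be randomized to 2 groups". I read the allocation sentence in the next section as 10 per group per centre.

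Protocol, Initial post-operative protocol, sets out the regimens:

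- Centre 1 brace arm: "At Center 1 (USA), patients will be initially kept non-weight bearing for a period of 8 weeks prior to applying an unloader brace".
- Centre 2 brace arm: "At Centre 2 (Japan), patients will wear an off-loading brace and commence weight bearing immediately post-operatively".
- Controls: "Non-bracing group will be NWB for 8 weeks at both centers".

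The section on Visit 1 repeats the timing, so it is not a slip: "Wearing of the brace will commence at the time of weight bearing, which will occur immediately post-operatively in Centre 2 (Japan" and at 8 weeks at Centre 1.

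The Background gives the aim as finding out whether the brace improves the results of microfracture. The SAP examines group differences with multilevel repeated-measures linear models, uses an adjusted threshold of .008, and aims to show superiority of the off-loading brace. It names no centre effect, no arm-by-centre term, no by-centre estimate and no restriction to one centre.

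The documents do not settle whether Centre 2 contributes analysed data. The Budget allows for MRI of 20 patients per study site, but the Imaging section names facilities at one US institution only: "The scans will take place at the Stanford Medical Outpatient Center" or a second imaging centre of the same institution.

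**The concern.** At Centre 1 the arms share the same loading for 8 weeks and then differ by the brace. At Centre 2 they differ by the brace, by when it starts, and by 8 weeks of weight-bearing. One pooled group coefficient cannot be read as the effect of the brace when half the planned patients come from a centre where brace and early loading arrive together.

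The Protocol itself treats loading as active. Its Background says that "protected weight-bearing for 8 weeks post-operatively protect the clot from shear forces, which may disrupt the clot and prevent healing", and also that "an unloading valgus brace may further enhance clot stability by protecting it from disruptive shear forces during motion". On that reasoning early loading could harm the repair while earlier bracing protects it, so the documents do not fix the sign of the difference between the centres' contrasts. A pooled null could hide a real benefit of bracing after week 8. A pooled benefit could be credited to the brace when loading, or the earlier start, contributed.

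**Working it through.** **The plan's own figure.** The only error-rate figure is .008. It reproduces as 0.05/6 = 0.0083; the family level of 0.05 and the divisor of 6 are inferred. It serves here only as the test level. The documents give no SD, effect size or power.

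**What the pooled coefficient estimates.** Let B1 be the Centre 1 contrast (brace from week 8 after non-weight-bearing, against no brace after non-weight-bearing). Let B1 + D be the Centre 2 contrast (brace plus weight-bearing from day 0, against no brace plus 8 weeks non-weight-bearing). D holds early loading, the earlier brace start and any other centre-by-arm difference. With Centre 2 share s:

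pooled = (1 - s)·B1 + s·(B1 + D) = B1 + s·D, with s = 20/40 = 1/2 as planned.

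A centre main effect or random intercept removes differences in level between centres. It does not remove s·D. For example, B1 = +0.5 and D = -1 give 0.5 - 0.5 = 0 at s = 1/2, 0.5 - 0.33 = +0.17 at s = 1/3, and 0.5 - 0.67 = -0.17 at s = 2/3.

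**Can a model separate brace from loading?** The design has four cells (centre by arm). Early loading occurs in one cell only, the Centre 2 brace arm, so its indicator equals the centre-by-arm product. Intercept, centre, arm and early loading have rank 4; adding centre-by-arm gives five columns and still rank 4. No model separates the two at Centre 2.

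**Standard errors**, in outcome SD, one measurement per patient, no dropout:

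- pooled, 20 v 20: sqrt(2/20) = 0.316
- one centre, 10 v 10: sqrt(2/10) = 0.447
- difference between the centres' contrasts: sqrt(4/10) = 0.632

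**Illustration of size** (B1 and D assumed; two-sided .008; s = 1/2; model with arm and centre):

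| B1 | D | Pooled effect | Rejection |
|---|---|---|---|
| 1.2 | 0 | 1.20 | about 83% |
| 1.2 | -1 | 0.70 | about 26% |
| 0 | +1 | 0.50 | about 11% |

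The last two rows come from simulating that model (20,000 trials: 26.6% and 10.7%). A noncentral t with residual SD 1 and 36 df gives 29.3% and 12.6%, which is too high for the pooled model. Leaving out the interaction shifts each cell by D/4 from the fit, so for D = ±1 the expected residual variance is 1 + 40·(1/4)²/37 = 1.068. A three-visit repeated-measures version with a centre term and within-patient correlation 0.3 to 0.7 gives 84%, 26–27% and 10–11%.

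**Could an interaction test justify pooling?** For D = 1 SD its power at .05 is about 34% (36 df), and about 28% with 20% dropout. A non-significant result would say little.

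**Price of using Centre 1 only for the brace claim.** Power for 1.2 SD at .008 falls from 83% to 46% if error df are borrowed from both centres (36 df), or to 41% on Centre 1 data alone (18 df). The 95% interval half-width rises from 0.64 to 0.91 (36 df) or 0.94 SD (18 df).

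**The case against.** Four points have force.

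First, the premise is unsettled. All three primary endpoints are MRI measures and the only scanners named are at one US institution. If Centre 2 supplies no analysed patients, the contrast is brace from week 8 against no brace with equal early loading, and the mixing disappears. This stands, and the point is conditional for that reason. The unconditional gap is that the SAP does not say which centres it covers.

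Second, a reader might infer that the pooled comparison is invalid or that randomisation has failed. The documents do not support that. Patients are randomised within centre, so each centre's whole-regimen comparison is sound, and so is their weighted average. The brace-only label is what fails. The Protocol's rule that bracing starts with weight-bearing even lends some support to reading the intervention as a brace-based strategy, but the Background and the SAP both state the aim as the brace.

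Third, a reader might take the 11% in the illustration as an inflated type I error. With B1 = 0 and D = +1 the Centre 2 regimen does have a 1 SD effect, so rejecting is a true finding about the average regimen. It is a false positive only for a claim about the brace alone.

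Fourth, the confounding at Centre 2 comes from the design, and no analysis removes it. That is correct. The SAP can only separate and label the two contrasts.

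**Conclusion.** The point holds, conditional on Centre 2 patients being analysed. In that case the SAP's group contrast estimates B1 + s·D, and crediting it to the brace goes beyond what the design allows. The algebra and the rank argument need no assumed values.

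The sizes do. The fall from about 83% to about 26%, and the 11% rejection rate, rest on assumed effects of 1.2 and 1 SD, 10 patients per arm per centre and no dropout. They show scale only and do not predict this trial. Nor do the documents support saying that the brace effect must be understated: the Background's argument leaves the sign of D open.

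This is an inexpensive improvement to the analysis and its labelling, not a fatal flaw. Confidence is medium, because the documents leave open which centres are analysed.

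**What to change.** 1. State in the SAP which centres supply analysed data and how many patients each provides. If only Centre 1 does, one sentence closes the matter.
2. If both do, fit arm, centre, visit and all their interactions up to arm-by-centre-by-visit, or analyse each centre separately. An arm-by-centre term alone would force the between-centre difference to be the same at every visit, so it does not give a 24-month contrast for each centre.
3. Report each centre's 24-month contrast with a confidence interval, labelled as the regimen comparison that centre actually made.
4. Limit any brace-only statement to Centre 1, and say that it concerns bracing begun after week 8.
5. Describe any pooled result as brace-based rehabilitation strategies against non-weight-bearing without a brace.
6. Do not use a non-significant interaction to justify pooling.
7. The SAP is written in the past tense. If the data have already been analysed, label the by-centre analysis post hoc.

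No new data are needed, but the cost is more than wording. The models must be rerun, and with three post-baseline visits the full model has 2 × 2 × 3 = 12 cell means from at most 40 patients. The brace-only estimate also loses the precision set out above. That is acceptable for estimates from a pilot, but it leaves little room for a confirmatory test at .008.

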Effects of Unloader Bracing in Clinical Outcome and Articular Cartilage Physiology Following Microfracture of Isolated Chondral Defects

Statistical Analysis Plan
NCT02016300

March 28, 2019

The primary endpoints were change in three MRI outcomes at 24 months: T2 relaxation times, repair region volume, and repair region thickness. Secondary endpoints included the KOOS sub-scores, the VR-12 score, the Lysholm score, and the Tegner score. For the primary and secondary endpoints, differences in the groups for T2 relaxation time, repair region volume, and repair region thickness and clinical outcomes were examined using multilevel, repeated measures linear regression models. A Bonferroni correction was used to adjust for multiple comparisons. The adjusted p-value was .008. We aimed to assess whether the data provided evidence of superiority of the off-loading brace in recovery after microfracture surgery.

Subgroup analyses examining correlations between questionnaire items and brace data were conducted with analyses limited to patients in the off-loading brace group. The number of days the brace was worn, the average number of minutes per day that the brace was worn, and the total number of minutes the brace was worn were calculated for patients in the off-loading brace group. Correlations were also examined between either the questionnaire items at each time point or the change from baseline to each time point in relationship to the total number of days the brace was worn or the total number of minutes the brace was worn over all days. Similarly, correlations were assessed between the MRI data at each time point and the change from baseline to each time point and the total amount of time the brace was worn. Data were analyzed using R and Rstudio (R Core Team, 2018; Rstudio Team, 2016). No interim analyses were performed.

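### No sentence in the plan places the first self-reported scores before allocation is known, and at Centre 2 the arms differ in weight bearing from the start.

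*Protocol*

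**What the plan says.** The timing is spread over four parts of the protocol.

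- **Recruitment.** Candidates are identified at a pre-operative evaluation. Eligibility depends on arthroscopy, so "final enrollment will occur immediately post operatively".
- **Initial post-operative protocol.** "Following enrollment, 10 patients will be randomized into one of two groups at each center". At Centre 2, "patients will wear an off-loading brace and commence weight bearing immediately post-operatively". For the comparison arm, "Non-bracing group will be NWB for 8 weeks at both centers".
- **Outcome Measures.** "Clinical outcome will be assessed at MRI follow-up time points using" KOOS, and Tegner, VR-12, Lysholm and VAS are listed after it.
- **First visit, in the appointment schedule.** Baseline and consent share one visit after surgery: "Visit 1 will be the baseline visit and will take place at the first post operative visit. Participants will undergo the informed consent process". The scores and the brace come later in that same visit, in this order: "Once signed, participants will answer standardized questionnaires (see above), get fitted for the brace (if in bracing group"). Baseline MRI and x-rays complete it. The later visits are at 6, 12 and 24 months.

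The SAP makes the KOOS sub-scores, VR-12, Lysholm and Tegner secondary endpoints and says that "clinical outcomes were examined using multilevel, repeated measures linear regression models". It neither defines baseline nor says how baseline enters those models.

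**The concern.** Patients know whether they have a brace, and the clinical scores are self-reported. A baseline score is safe for comparing arms only if the arm cannot have influenced it. That means it must be recorded before the patient learns the allocation and before care differs between arms.

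Here the first score is taken after surgery, at a visit with no stated day, in a plan that also places randomisation somewhere after surgery. If the arm is known first, expectation can colour the answers. At Centre 2, different weight bearing can also change the symptoms and function being scored. An analysis that uses this score as baseline would then carry part of the arm effect into the reference value.

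**Working it through.** **1. Consent and randomisation.** Randomisation follows enrolment, and in ordinary usage a patient is not enrolled without consent. The most coherent reading is therefore that enrolment is the consent given at Visit 1, with randomisation after it and before brace fitting. The two stated timings (immediately after surgery, and the first post-operative visit) agree only if Visit 1 is very early. The protocol does not say that it is.

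**2. Questionnaires and randomisation.** The Visit 1 text lists consent, then questionnaires, then fitting for those in the brace group. At most this puts the scores before fitting. It does not put them before the patient knows the arm, and a fitting conditional on group membership is equally compatible with an arm already assigned. No other sentence in either document addresses this order.

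**3. The two centres.**

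- *Centre 1.* Both arms are non-weight-bearing for 8 weeks, and the brace is worn only from then on. At an early Visit 1, only knowledge of the arm could affect the scores.
- *Centre 2.* The arms differ from the start. If the timing is taken at its word, there are two possibilities. Either Visit 1 happens straight after surgery, and the scores can precede the divergence, or it happens later, and the scores follow it.

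**4. Pre-operative scores.** The clinical scores are tied to the MRI time points. The visits are T=0 (post-operative), 6, 12 and 24 months, and none is before surgery. The protocol says that Tegner will describe activity before and after treatment, but no pre-operative collection is scheduled, and treatment there may mean the brace.

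**5. Size.** The plan states no figure to reproduce. The following is illustrative only.

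- From the protocol: 10 patients per arm at each of 2 centres, so 20 per arm. The standard error of an arm difference at one time point is sqrt(1/20 + 1/20) = 0.316 SD.
- Assumed: the arm shifts one group's Visit 1 score by s = 0 to 0.3 SD, and the baseline-outcome correlation is rho = 0.1 to 0.6.
- If baseline is not used in the model, the contrast does not move.
- If change from baseline is compared, it moves by s, that is 0 to 0.30 SD, opposite in direction to the baseline shift.
- If baseline is a covariate, it moves by rho × s. At s = 0.3 this is 0.1 × 0.3 = 0.03 SD to 0.6 × 0.3 = 0.18 SD, so the whole range is 0 to 0.18 SD.
- If only Centre 2 is affected (10 of the 20 in the arm), the pooled figures are about half: 0 to 0.15 SD and 0 to 0.09 SD.

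The SAP does not say which of these forms the models take.

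**The case against.** The strongest reply is that the text already gives a workable order. Patients are randomised after enrolment, enrolment implies consent, and a brace cannot be worn before it is fitted, which happens after consent at Visit 1. If Centre 2 patients wear the brace immediately, Visit 1 must be about that early, and randomisation can sit between the questionnaires and the fitting. For consent, most of this stands. For the questionnaires it shows that a sound order is possible, not that one is required.

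The reply is also right that eligibility is settled only at arthroscopy. That justifies late randomisation, but it does not require late consent or late scoring. A separate consent form could fix an earlier time; the protocol's own schedule would still need to agree with it.

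A reader might infer more than the documents support:

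- *That patients are randomised before consenting, so selective refusal threatens every endpoint, including the primary MRI ones.* No sentence says this, and the enrolment wording points the other way. It remains a lesser, unproven possibility.
- *That the brace-wear correlations are distorted by allocation order.* They are confined to the brace group. A shift shared by everyone in that group leaves a correlation unchanged.
- *That lacking a pre-operative score itself biases the comparison or loses precision.* A post-operative score taken before allocation does not bias the randomised contrast. With the same assumed correlation range for either baseline, the residual-variance ratio (post-operative to pre-operative) runs from (1 − 0.36)/(1 − 0.01) = 0.65 to the inverse, 1.55. The direction is therefore unknown.
- *That the MRI baseline should move before surgery.* A post-operative scan is the proper reference for the repair region.

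**Conclusion.** The point stands as a missing safeguard, not as demonstrated bias. The plan does not ensure that the first self-reported scores precede knowledge of the arm. On its stated schedule, the Centre 2 scores are taken either straight after surgery or once the arms have diverged in weight bearing. The risk falls mainly on the self-reported secondary scores, and only in so far as the models use the Visit 1 score as baseline.

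No size follows from the documents. The illustrative ranges rest wholly on the assumed shift and correlation, and both include zero. Their upper ends, 0.30 and 0.18 SD, are not negligible beside a standard error of 0.316 SD. The correction should be made because it is cheap and removes the risk. Confidence is medium, because a sound order may have been intended.

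**What to change.** Take consent and one full questionnaire set at the pre-operative evaluation where candidates are already identified. Confirm the lesion at arthroscopy, and randomise only then. State this order in the protocol. In the SAP, name the pre-operative score as the baseline covariate in the clinical-score models. Keep the post-operative MRI as the imaging baseline, taken before brace wear or weight bearing starts at either centre.

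At minimum, one sentence would do: randomise at Visit 1 only after consent and questionnaires are complete, and before fitting or weight bearing.

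The cost is earlier consent and one questionnaire set at an evaluation that already takes place. The drawback is that some patients will consent, complete the questionnaires and then prove ineligible at arthroscopy. For patients already operated on, a pre-operative score cannot be recovered. For them, report the actual order of consent, scoring and randomisation by centre, and any refusals by arm.
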